Subjects will be consented using a current informed consent form that has been approved by the respective study site's Institutional Review Board. Subjects will be allowed adequate time to read the informed consent, discuss the consent with study staff and others (e.g., family members, friends, or any of their health care providers), and have their questions answered prior to signing the informed consent. In some cases, a site may not accrue study subjects but serve as a data analysis site so informed consent may be waived for that site.

Site-specific recruitment plans and consent process are outlined in Attachment L1.

E2.e Randomization Method and Blinding

Subjects that would normally be selected to receive a TAP block will be randomly assigned into one of the three arms. A random number generator will be used to generate an equal proportion of responses of the three arms. These responses will be sealed in envelope. The anesthesia provider will be allowed to open the envelope and become aware of the selected arm after the initiation of anesthesia (this would include the administration of a pre-medication or initiation of general anesthesia). Complete blinding is impossible to staff given the visual presence of a catheter in some groups versus the lack of catheters in other groups. In addition, the agent Exparel® has a milky color that is obvious to the anesthesia provider injecting it. However, the nursing staff on the floor will not be made aware of the use of Exparel® versus Bupivacaine in the single injection arms.

E2.f Risks and Benefits

i Risks

Potential physical risks include:

TAP block is a relatively low risk regional anesthesia technique with a long track record. However, any injection or insertion of a catheter into the body carries a slight risk of bleeding, bruising at injection or insertion site, and infection at injection or insertion site. Risks particular to an injection of a local anesthetic into the abdominal area would be bowel perforation, local anesthetic toxicity, and drug allergy. These risks are unlikely and similar to an abdominal paracentesis. Furthermore, the author is unaware of any episodes of bowel perforation from the administration of a TAP block.

The following are side effects have been seen with the local anesthetics Bupivacaine and Ropivacaine:

- Low blood pressure
- Nausea and/or vomiting
- Slow heartbeat
- Fever
- Pain
- Post-operative complications
- Low blood hemoglobin (anemia)

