Subjects may be withdrawn from the study early due to complications secondary to the surgery itself such as sepsis, bowel dysfunction unrelated to narcotic use, and the need for further exploratory surgery.

Catheter dysfunction due to dislodgment or severe leakage may also precipitate early withdrawal from the study. Bleeding, infection, or need to anti-coagulate may cause premature need to remove the catheters from the patients. In these cases, the data will continue to be recorded as in the other arms; however, time of catheter removal will also be recorded.

Failure to perform an adequate block will also cause withdrawal from the study. Reasons for said failure would include: inability to visualize TAP space on ultrasound and surgical site preventing use of bilateral TAP block.

Failure to place catheter after successful bolus of local anesthetic would move patients from the CTAP group to an un-randomized single shot Bupivacaine arm. Patients will be followed until completion of the study. This data may be analyzed separate or as part of the single shot Bupivacaine group.

Failed block is a withdrawal prior to first study follow up; these patients would need to be replaced or moved to an open un-randomized arm.

Subjects may also be withdrawn from the study if at any time it is determined that they did not meet inclusion exclusion criteria.

iii Subject safety

iv Non-compliance with study visit schedule or study regimen

Subjects may be involuntarily exited from the study for failure to comply with the protocol, failure to attend follow-up visits, or for other reasons. The investigator shall arrange for an exit visit and complete the case report form for the subject to the extent there is data available.

Subjects may voluntarily withdraw from the study at any time without reason. The investigator shall make an effort to obtain an exit visit and complete the case report form for the subject to the extent there is data available. The investigator cannot require that an exit interview take place.

E2.g Data Collection and Follow-up for Withdrawn Subjects

- 1) Reason for withdrawal from study (i.e. block failure, catheter failure, drug toxicity, sepsis, patient request)
- 2) Day of withdrawal from study

Study Drug/Device

E3.a Description

The ON-Q[®] device is considered a non-significant risk device which has been marketed for postoperative pain management since 1998.

Description of Device:

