All post-surgical patients are given a Dilaudid (or the equivalent dose of Morphine if not tolerated) IV PCA with every 10 minutes bolus function following surgery to be initiated immediately upon admission and transfer from the PACU to the floor. A clinician bolus of Dilaudid 0.5 mg every 30 minutes will be made available for additional pain control if needed.

Acetaminophen (Tylenol) will also be made available for treatment of post-operative pain on the floor.

Treatment Regimen

Patients assigned to the study group will randomly be assigned to one of the three arms described above. Patients in the catheter arm will receive a commercially available ON-Q® pain management system filled with 0.2% Ropivacaine. The ON-Q® system consists of an ON-Q® elastomeric infusion pump that will be connected to an end-orifice catheter. Patients in the catheter arm will receive a 20 ml bolus of Bupivacaine via Tuohy needle in the TAP space followed immediately by tunneling of a catheter into the TAP space under ultrasound guidance prior to extubation and complete emergence from general anesthesia. Said catheter will be left to infuse continuous local anesthetic site up to post-operative day 3. Patients in the two (2) single injection arms will similarly receive a bilateral injection of study local anesthetic (Exparel or Bupivacaine) 25-30ml per side in the TAP space prior to the conclusion of surgery under ultrasound guidance. Intra-operatively patients in all three study arms will receive IV fentanyl and IV Acetaminophen 1000mg unless drug allergy or intolerance to either medication.

Initial rescue IV pain medication will be made available similarly in all three study arms according to the institution's protocol for PACU breakthrough pain and will consist primarily of IV Dilaudid (or Morphine equivalent if patient does not tolerate Dilaudid). All post-surgical patients are given a Dilaudid (or Morphine if not tolerated) IV PCA with q10min bolus function following surgery to be initiated immediately upon admission and transfer from the PACU to the floor. A clinician bolus of Dilaudid 0.5 mg every 30 minutes (or Morphine equivalent) will be made available for additional pain control if needed. Tylenol will also be made available for treatment of post-operative pain on the floor.

E3.b Method for Assigning Subjects to Treatment Groups

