Randomization will occur following the consent process and prior to surgery. The on-site personnel will manage the randomization. A random number generator will be used to assign patients to one of three arms and the anesthesia provider will be unaware of which arm the patient is assigned to until after initiation of anesthesia (see section E2.e).

E3.c Preparation and Administration of Study Drug

Patients in the single shot arms (Bupivacaine 0.25% and Exparel) will receive bilateral bolus injections of the local anesthetic t prior to extubation (waking up from General Anesthesia). Patients in the continuous catheter arm will also receive a bolus injection of local anesthetic prior to the placement of the catheter. Those patients will also receive a pump.

- 1) Bupivacaine 0.25% Arm: A total of 60 ml Bupivacaine 0.25% from two 30 ml vials will be pre-drawn up via 60 ml Syringe. The syringe will be connected and a 10ml flush syringe containing 10ml 0.9 NS will be connected to the end of an IV extension set via a 3-way stopcock and luer lock connections. The Bupivacaine 0.25% syringe will also be connected to the stopcock. The distal end of the IV connection will be maintained sterile and will be connected to the injection needle. Then the procedure is as follows: Step 1) The entire setup will be flushed with 0.9NS via flush syringe. 2) The TAP space will be located under ultrasound guidance and verified by using the 0.9% NS flush syringe. Once in the TAP space, 30 ml Bupivacaine 0.25% will be injected into the TAP space (This dose will be decreased to 25ml for patients under 70 kg). Steps 2 and 3 will be repeated on the opposite side TAP block.
- 2) Exparel Arm: The entire contents of one 20 ml Exparel vial (266 mg) will be drawn up 20 ml syringe. 40ml Bupivacaine 0.25% will be pre-drawn into 2x 20 ml syringes and connected to a stopcock. The syringe containing the Exparel solution will also be connected to the stopcock. The distal end of the IV connection will be maintained sterile and will be connected to the injection needle. Procedure Step: 1) The entire setup

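### The allocation envelope may be opened before block feasibility is judged, so patients can be excluded for block failure by a provider who already knows the arm

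*Combined protocol and SAP*

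**What the plan says.** **When the arm is revealed.** E2.e (Randomization Method and Blinding) allows the provider to "become aware of the selected arm after the initiation of anesthesia" and explains that "this would include the administration of a pre-medication or initiation of general anesthesia". E3.b agrees: "the anesthesia provider will be unaware of which arm the patient is assigned to until after initiation of anesthesia". Neither section asks for concealment beyond that moment.

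**When the block is done.** Treatment Regimen has the single injections given "25-30ml per side in the TAP space prior to the conclusion of surgery under ultrasound guidance", and the catheter placed before extubation and full emergence. E3.c has the single injections before extubation. The data form in Attachment L offers tick boxes for both pre-incision and post-incision.

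**What happens when a block fails.** Early Withdrawal of Subjects makes an inadequate block a reason for withdrawal. The reasons it names are "inability to visualize TAP space on ultrasound and surgical site preventing use of bilateral TAP block". It treats a failed block as a withdrawal before first follow-up, with the patient replaced or moved to an open un-randomized arm. A patient whose catheter cannot be placed after the bolus moves to an un-randomized single-shot group. E2.g lists only the reason and day of withdrawal as data to collect.

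**How such patients are analysed.** The Statistical Analysis Plan states intention-to-treat on all randomized participants. Missing Outcome Data leaves missing data out and allows extra recruitment into one or more arms.

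**Opioid given in theatre.** Treatment Regimen says "Intra-operatively patients in all three study arms will receive IV fentanyl", with no amount or dosing rule. The form's fentanyl row has columns for PACU and POD 0 to 3 only.

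**The concern.** Concealment protects a randomised comparison only if nobody who knows the arm decides who stays in the trial. Here two decisions that end participation rest on the operator's judgement: whether the TAP space can be seen, and whether the surgical site permits a bilateral block. Both may be made with the arm known.

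The protocol itself gives a reason why thresholds might differ by arm. The abstract says that a catheter takes more skill and time than an injection, and E2.b excludes BMI above 40 because catheters are hard to place. A provider facing a marginal view could persist with an injection and give up on a catheter without intending any bias. If the patients removed differ in expected opioid need, the arms are no longer comparable on the primary outcome, total postoperative narcotic over 48 hours (Primary Aim).

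A lesser matter is that theatre fentanyl is also given in a period when the arm may be known, and the form does not capture it, so an arm difference could not be seen afterwards.

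**Working it through.** **Sequence of events, from the sections above**

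1. Consent, then randomisation before surgery (E3.b). The arm is concealed.
2. Premedication or induction. The envelope may be opened (E2.e).
3. An interval of unspecified length. It is short if the block is pre-incision and may be long if it is done late in the case.
4. Judgement of block feasibility. No section requires this before step 2.
5. If the block is judged not possible: withdrawal before first follow-up, with replacement or a move out of the randomized arms.
6. Analysis: all randomized in principle, but missing outcomes are omitted.

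Steps 2, 4 and 5 together permit arm-aware exclusion. Step 6 does not restore these patients if no outcome was collected.

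**The plan's own figure.** The point disputes no figure, but the planning values are used below. With a difference of 4.1 − 2.4 = 1.7 mg, SD 3 mg, two-sided 0.05 and 80% power:

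n = 2 × (1.960 + 0.842)² × 3² / 1.7² ≈ 48.9, so 49 per arm, as stated. The plan recruits 159 / 3 = 53 per arm, taken here as given.

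**How many patients are exposed.** Assumed block-failure rate 5–10%, because the documents give none:

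- 53 × 0.05 = 2.65, about 3 per arm
- 53 × 0.10 = 5.3, about 5 per arm

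This counts every failure, not the failures influenced by knowledge of the arm.

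**Illustration of possible bias.** Suppose only one arm loses a fraction f, and those removed differ from that arm's mean by c standard deviations. The remaining mean moves by 3 × c × f / (1 − f) mg. The two-sided type I error uses SE = 3 × √(1/53 + 1/(53(1 − f))). Both f and c are assumptions, SD stays at 3 mg, and replacement is not modelled.

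| f | c | shift (mg) | share of 1.7 mg | type I error |
|---|---|---|---|---|
| 2% | 0.5 | 0.031 | 1.8% | 0.050 |
| 2% | 1.0 | 0.061 | 3.6% | 0.051 |
| 5% | 0.5 | 0.079 | 4.6% | 0.052 |
| 5% | 1.0 | 0.158 | 9.3% | 0.058 |
| 10% | 0.5 | 0.167 | 9.8% | 0.059 |
| 10% | 1.0 | 0.333 | 19.6% | 0.086 |

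Similar losses in all arms would largely cancel. The last row is an unfavourable case, not an expectation.

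**The case against.** The strongest reply is that later opening treats a symptom. Randomisation precedes surgery, so patients who fail a feasibility check are still lost after randomisation, and the most arm-dependent failure, inability to place the catheter, can never be judged blind. On this view the real defect is withdrawal and replacement set against the intention-to-treat statement. Much of this stands, and the fix therefore also requires follow-up and analysis of everyone whose envelope is opened. But exclusions made with the arm concealed cannot depend on the arm, which is the gain from judging feasibility first.

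It is also fair to say that the two listed reasons are not specific to any arm, that early opening is permitted but not required, and that no section says that one person opens the envelope, gives the fentanyl and judges the block. That is the natural reading, not an explicit statement. Concealment through consent and enrolment is intact.

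Two stronger readings are tempting and are not supported:

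- A reader might infer that every block is done near the end of surgery, leaving a long arm-aware interval in every patient. The text sets only outer limits, and the form has a pre-incision box.
- A reader might infer that arm-aware fentanyl dosing biases the primary outcome directly. Theatre fentanyl is not part of the 48-hour postoperative total. Any effect would act indirectly, through early postoperative need, and the documents give nothing from which to size it.

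**Conclusion.** The plan allows the two listed block-failure judgements to be made with the arm known, and removes the patients concerned from the randomized comparison. The intention-to-treat statement does not cure this while such patients leave before first follow-up and missing outcomes are dropped.

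About 3–5 of 53 patients per arm would be open to such exclusion if 5–10% of blocks fail. The resulting bias cannot be estimated from the documents. Under the one-sided losses illustrated it runs from 0.03 to 0.33 mg against a 1.7 mg target. That is modest, and it is cheap to avoid. For fentanyl, the supportable conclusion is only that the form should record it so that balance can be checked.

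**What to change.** - **E2.e and E3.b:** whenever the block is done, the provider first checks and records on ultrasound that the TAP space is visualized on both sides and that the surgical site permits a bilateral block. The envelope is opened only after that, immediately before the block is prepared. Patients who fail the check are excluded with the arm still concealed, and are counted and reported.
- **Early Withdrawal, Statistical Analysis Plan and Missing Outcome Data:** everyone whose envelope is opened, including failed catheter placements, stays in follow-up and is analysed by intention-to-treat in the assigned arm. Because randomisation precedes surgery, the definition of the analysis set must state the concealed exclusions explicitly.
- **Data form:** add total intra-operative fentanyl and summarise it by arm.
- **Block timing:** the sponsor should reconcile Treatment Regimen, E3.c and the form's pre-/post-incision boxes. No timing is proposed here.

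The cost is a few sentences, one form field, a brief bilateral scan before opening, and perhaps a few minutes to prepare arm-specific supplies. The scan is an added step, because E3.c has the space located through an arm-specific syringe set-up. The planned sample size and the treatments do not change. Catheter-threading failure still cannot be judged blind, so retention in the assigned arm has to deal with it.

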will be flushed with the Bupivacaine syringe. 2) The TAP space will be located using the Bupivacaine syringe under ultrasound guidance. 3) Once the TAP space, Exparel 133mg will be injected into the TAP space. 4.) After injection, the syringe will be exchanged for the Bupivacaine syringe and the residual Bupivacaine will be injected into the space (~20ml). Steps 2-4 will be repeated for the opposite side TAP block.

- 3) Continuous Catheter Arm: A total of 40 ml Bupivacaine 0.25% vials will be pre-drawn up via two 20 ml Syringes. The Bupivacaine 20ml syringe will be connected to IV tubing. The distal end of the IV connection will be maintained sterile and will be connected to the injection touhy needle. Procedure step 1) The entire setup will be flushed with the Bupivacaine syringe. 2) The TAP space will be located using the Bupivacaine syringe and ultrasound guidance. 3) Once in the TAP space, 5-10ml Bupivacaine 0.25% will be injected into the TAP space. The IV extension will then be disconnected from the touhy needle and a catheter will then be threaded via the touhy needle and into the TAP space. The proximal end of the catheter will then be connected to the distal end of the IV extension set and the residual Bupivacaine 0.25% from the 20ml syringe will then be injected thru the catheter. The catheter will then be secured and dressed via standard technique for catheter placement. Steps 2-4 will then be repeated for the opposite side TAP block. In the PACU, patients will receive a pre-filled ON-Q[®] system obtained through the hospital pharmaceutical department. The pre-filled ON-Q[®] system contains Ropivacaine 0.2% in a 700 ml container. The infusion pump will be set to run at a rate of 7 ml/hr. per side.

Breakthrough pain will be managed similarly in all three arms via Dilaudid IV PCA every 10 minutes with clinician bolus function of 0.5 mg every 30 minutes.

E3.d Subject Compliance Monitoring

The Principal Investigator will oversee compliance with study procedures.

E3.e Prior and Concomitant Therapy

N/A

E3.f Packaging/Labeling

N/A

E3.g Blinding of Study Drug

It will be impossible to blind the catheter group from practitioners and floor care nurses given the obvious appearance of the catheters. However, the floor care nursing and staff will be blinded between the single injection arms: Exparel and Ropivacaine. The

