anesthesia provider placing the block will similarly not be blinded given the need to place the catheters and the milky coloration of the Exparel drug when compared to Bupivacaine.

E3.h Receiving, Storage, Dispensing and Return

Study medications will be dispensed from the pharmacy according to usual procedures.

F Study Procedures

Screening for Eligibility

We will review the patient's medical records to determine study eligibility prior to obtaining consent of the patient to participate in the study. No research-specific information will be collected prior to the informed consent process.

The site-specific screening procedures are outlined in Attachment L1.

Schedule of Measurements

See Attachment L2 for a Table of the Schedule of Measurements/Calendar.

Safety and Adverse Events

F3.a Safety and Compliance Monitoring

The lead study investigator will monitor the safety and compliance of all study sites utilizing the Oncore ERM study management system.

F3.b Medical Monitoring

i Investigator only

This study is a comparison of three usual care regimens for the prevention and treatment of post-operative pain. The Investigator will be responsible for all medical monitoring through the course of providing usual patient care.

ii Independent expert to monitor

The Human Research Protection Program of Medicine and Science monitors all investigator-initiated research. Reports of monitoring visits are provided to the Principal Investigator and the Director of HRPP.

iii Institutional Data and Safety Monitoring Board

The Institutional Review Board will provide safety oversight for this study.

iv Independent Data and Safety Monitoring Board
No Independent Data and Safety Monitoring Board will be created for this study.

F3.c Definitions of Adverse Events

Adverse events will comprise all events that are untoward changes from a subject's baseline condition.

3.d Classification of Events

i Relationship

The investigator will determine the relationship of an adverse event to the TAP Block procedure.

ii Severity

The Investigator will assess the severity of adverse events in accordance with the Common Terminology Criteria for Adverse Events (CTCAE) version 4.03.

iii Expectedness

Adverse events listed in the protocol, IRB-approved informed consent form, or drug specific, FDA-approved package inserts will be considered to be foreseeable risks of participation in the study. Other adverse events will be considered unexpected.

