F3.d Data Collection Procedures for Adverse Events

Please see Attachment L2 for data collection form. All adverse event data will be entered into Oncore ERM.

F3.e Reporting Procedures

Serious Adverse Events and adverse events that meet "severe" criteria must be directly reported within 24 hours to the Principal Investigator, and the IRB.

[name] M.D.
[contact]
[contact]
Department of Anesthesiology
Midwestern Regional Medical Center
Zion, IL

Other adverse events must be entered within 7 days of collection into the Oncore ERM.

F3.f Post-study Adverse Event

Serious Adverse Events and adverse events that meet "severe" criteria must be directly reported within 24 hours to, the Principal Investigator and the IRB.

[name] M.D.
[contact]

[contact]
Department of Anesthesiology
Midwestern Regional Medical Center
Zion, IL

Other adverse events must be entered within 7 days of collection into the Oncore ERM.

F3 Study Outcome Measurements and Ascertainment

G Statistical Plan

Interim Monitoring and Early Stopping

The Principal Investigator will utilize the Oncore ERM study management system to monitor the study.

The study may be stopped early for the following reasons:

- withdrawal of funding
- safety issues
- drug has been proven effective and no further testing is needed

Analysis Plan

The study is a prospective, randomized, open, active controlled clinical trial. Effectiveness of the Continuous TAP (CTAP) via the ON-Q[®] Pain Management System will be evaluated and compared to single shot techniques with respect to reductions in postoperative opioid consumption over the first 72 hours postoperatively. Secondary outcomes including hospital length of stay (LOS), time in PACU, pain at rest and with activity, return of bowel function, and incidence of opioid related side effects will also be evaluated.

The aims of this study are to compare the efficacy of continuous TAP block via ON-Q[®] system versus that of single injection techniques for TAP block regarding opioid reduction among patients undergoing major abdominal surgery. It is hypothesized that a continuous TAP block technique reduces pain, the need for opioids as well as the expected length of stay relative to those resulting from those subjects receiving a single TAP injection of Exparel (liposomal Bupivacaine) or single TAP injection of Ropivacaine to treat postoperative pain.

Study success criteria:

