Patient characteristics and outcomes data will be summarized by cross-tabulation (categorical variables), quartiles (median, ordinal variables), and mean and standard deviation (continuous variables). Comparisons between groups will use Chi-square test or Fisher's exact test as appropriate for categorical variables and t-test or Wilcoxon rank-sum test as appropriate for continuous variables.

Analyses of primary outcome will examine differences in mean opioid consumption between the single shot TAP group and the Exparel TAP group. Analyses of secondary outcomes will examine differences in mean opioid consumption between the single shot TAP group and continuous TAP group. Treatment groups will be compared using a

student's t-test if data are normal distributed or Wilcoxon rank-sum test if not normal distributed.

The differences in mean opioid consumption across three groups (single shot TAP, continuous TAP, and Exparel TAP) will be examined with a test of means between groups using one-way analysis of variance (ANOVA). A comparison between continuous TAP and Exparel TAP will be performed. A t-test will be used if the observations in each trial arm are normally distributed; if non-normally distributed, then rank-based methods such as Wilcoxon rank-sum test will be employed.

All tests will be two-sided.

The overall incidence of serious adverse events and adverse events and number and proportion of patients reporting such events will be summarized by treatment group. Adverse events will be tabulated and summarized by the number and percentage of subjects who experienced the event.

Missing Outcome Data

Analysis will be conducted as described in prior section. Missing data will not be included in the analysis; however, may lead to an increase in patients recruited into one or more study arms.

Unblinding Procedures

This study is not blinded because it will be obvious to all care givers whether or not the patient received a continuous block with catheters or not.

H Data Handling and Record Keeping

Confidentiality and Security

Data will be collected on the data collection forms located in Attachment L9 and entered into the Oncore ERM study management system.

Data collection forms will be stored at each respective study site within a locked cabinet in a locked research office.

The Oncore ERM study management system is a secure web-based management system that is password-protected. Access to data is role-specific.

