Schedule of Measurements Template (add additional information as needed)

Anesthesiologist performing TAP BLOCK	Surgeon
Date of Surgery	Hospital Discharge Date
Procedure  Ventral hernia  Expl. Lap  Colon  Small Bowel  Anterior Resection  APR  Lower Anterior Resection  Prostate  TAH  HIPEC  Cyto-reductive Surgery  Ileostomy reversal  Robotic Assisted +/- Hand Assisted  Robotic (no incision)  L/S Assisted +/- Hand Assisted  L/S (no incision)  Other _____	 Continuous TAP with Ropiv 0.2%  Single Shot TAP  Exparel  0.25% Bupivacaine  Pre-incision  Post-incision Other: _____

PATIENT INFORMATION

Initials	Outpatient / SDA  Patient taking narcotics at home prior to surgery?  Yes  No	Inpatient (prior to Surgery)  PCA  IV narcotics  (skip if PCA) P.O. Narcotics  (skip if PCA)	
Age	Gender  M  F	Race  Cauc  Black (Non Hisp)  Hisp  Asian  Other	ASA
BMI	Smoking  Yes  No	Diabetes  Yes  No	
Incisional Dermatone Level Range: (Umb=T10)	Surgery Duration (minutes)	PACU Time until nurse gives report	

Outcomes	PACU	POD 0	POD 1	POD 2	POD 3
PCA		 Y  N	 Y  N	 Y  N	 Y  N
NARCOTICS					
MSO4 (mg) total requirements					
Dilaudid (mg) total requirements					
Fentanyl (mg) total requirements					
Anti-emetic Given (+/-)					
EVENTS					
Bowel Movement (+/-) (record 1 st day only)					

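### For Exparel versus single-shot bupivacaine, the protocol masks only floor nursing and staff and makes no provision to mask patients, PACU staff or outcome recorders

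*Combined protocol and SAP*

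**What the plan says.** Four places address masking.

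- **E2.e, Randomization Method and Blinding.** Complete blinding of staff is called impossible because catheters are visible and Exparel looks milky to the person injecting it. One exception follows for the two single-injection arms: "the nursing staff on the floor will not be made aware of the use of Exparel® versus Bupivacaine".
- **E3.g, Blinding of Study Drug.** The exception is worded more widely: "the floor care nursing and staff will be blinded between the single injection arms: Exparel and Ropivacaine". By contrast, it says that the "anesthesia provider placing the block will similarly not be blinded".
- **Section G, Analysis Plan.** "The study is a prospective, randomized, open, active controlled clinical trial".
- **Section G, Unblinding Procedures.** One statement covers the whole trial: "This study is not blinded because it will be obvious to all care givers whether or not the patient received a continuous block with catheters". No exception is made here for the single-injection arms.

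Sample Size and Statistical Analysis Plan (section G) make single shot versus Exparel the comparison for the sample size and the primary analysis. The Primary Aim (section C) names it as one of two comparisons, the other being catheter versus single shot.

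The data form under section L offers tick-boxes for Exparel and "0.25% Bupivacaine". The same form holds the PCA, opioid and pain-score fields.

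**The concern.** The case against blinding is built on the catheter arm and then applied to the whole trial. Between the two single-injection arms there is no catheter, and the milky color is visible only to someone who sees the syringe. The protocol treats masking as worthwhile here, since it masks the floor staff, but it does not extend this to the patient.

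The patient matters most. Under Treatment Regimen, rescue is an IV PCA with a bolus available every 10 minutes, plus a clinician bolus if needed. Pain is self-rated on a 0-10 scale. A patient who knows they received a drug described as acting for three days may press less often and score lower. The protocol accepts that kind of mechanism in E2.f, where it notes that seeing a leaking catheter may change the pain a patient reports. A PACU nurse who knows the arm may dose differently, and a recorder who knows it may rate or prompt differently. Any of these could produce part of the observed difference without a drug effect.

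**Working it through.** **1. Who is masked between the two single-injection arms**

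| Group | Provision in the protocol | Do the stated reasons apply? |
|---|---|---|
| Floor nursing and staff | Masked (E2.e, E3.g) | No |
| Anesthesia provider | Expressly unmasked (E3.g) | Yes: sees the drug |
| Patient | None | No |
| PACU staff | None | No, unless they see the syringe |
| Outcome recorders | None, and not identified | No, unless they see the syringe or the arm box |

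**2. Could the patient tell the arms apart?** E3.c places both injections before extubation. Volumes per side are close. For Exparel, half of a 20 ml vial (133 of 266 mg) is 10 ml, plus about 20 ml bupivacaine, so about 30 ml. For bupivacaine it is 30 ml, or 25 ml under 70 kg. Under E2.e the provider learns the arm only after anesthesia has been initiated. That can be as early as pre-medication, so the patient may still be awake at that moment, but nothing requires the patient to be told.

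**3. The form.** The arm box and the outcome fields are on one form, so whoever completes it can see the arm.

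**4. The plan's sample size.** Inputs from Sample Size: difference 4.1 − 2.4 = 1.7 mg, SD 3 mg, two-sided alpha 0.05, power 80%.

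n = 2 × SD² × (1.960 + 0.842)² / difference² = 2 × 9 × 7.85 / 2.89 = 48.9, so 49 per arm. This matches the plan. Masking does not change it.

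**5. Illustration of what a bias would do.** The documents give no bias size. Assume no true drug effect and that knowledge of the arm lowers Exparel use by b = 0.3 or 0.6 mg (18% or 35% of 1.7 mg).

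SE = 3 × √(2/49) = 0.606 mg. The chance of a significant result is approximately Φ(b/SE − 1.960) + Φ(−b/SE − 1.960).

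- b = 0.3: b/SE = 0.495; 0.0715 + 0.0070 = 7.9%. The exact t-test (96 df) gives 7.8%.
- b = 0.6: b/SE = 0.990; 0.1660 + 0.0016 = 16.8%. The exact t-test gives 16.5%.

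With the plan's separate SDs of 3 and 1.3 mg, SE = √((9 + 1.69)/49) = 0.467 mg, and the t-test figures are 9.7% and 24.6%. The common SD of 3 mg therefore gives the milder result.

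**The case against.** The protocol declares an open trial whose arms follow common practice, and an open design is a legitimate choice. That stands as a general defense, but the reasons actually offered do not cover this comparison.

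Some stronger readings are tempting, and the documents do not support them.

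- **That patients and recorders will know the arm.** Nothing says that they are told. This would be an inference from the open label and from silence. The consent form and the site-specific attachment on consent, neither of which is in the text available, may say what patients are told.
- **That only nurses are masked.** E3.g adds staff, which could include some recorders. The documents do not say who records outcomes.
- **That the form undoes the nurse masking.** This would need floor nurses to complete or see the form, and nothing says that they do. Abstraction from the chart by research staff fits the form equally well.
- **That clinician boluses on the floor are exposed.** If floor nurses give them, they are masked between these arms. The staff-driven gap is in the PACU.
- **That masking here protects the whole primary question.** The Primary Aim also includes catheter versus single shot, and the success criterion centers on the catheter, which cannot be masked from staff in the same way.

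**Conclusion.** The point holds as a gap in provision. For the comparison on which the sample size and primary analysis rest, the protocol masks floor nursing and staff and provides nothing for patients, PACU staff or recorders, although its reasons against blinding do not apply to them. Unblinding Procedures also denies, without exception, the masking that E2.e and E3.g promise.

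The rates of 7.8% and 16.5% rest on an assumed bias of 0.3 and 0.6 mg, no true effect, 49 per arm and SD 3 mg. They show how sensitive the test is. They are not evidence that bias will occur, and they apply only if knowledge of the arm reaches the patient or the staff who influence the outcome.

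This should be changed, because masking cannot be restored for a patient who has already learned the arm. It does not by itself invalidate the design.

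**What to change.** 1. In E2.e and E3.g, state that patients in the two single-injection arms are told only that they received a single-injection TAP block until the 72 h assessment is complete. State also that PACU staff, floor staff and the existing outcome recorders are not told which drug was used.
2. Move the arm tick-box to a separate page kept by the anesthesia provider.
3. Reword Unblinding Procedures to say that the catheter arm is unmasked, that the anesthesia provider is unmasked in all arms, and that patients, staff and recorders are masked between the single-injection arms. Confining the words on not being blinded to the catheter arm would not do, because it would contradict E3.g on the anesthesia provider. Bring the open label in the Analysis Plan into line.
4. Add an emergency unmasking route.
5. Reconcile the name of the single-injection comparator: E3.g says ropivacaine, while E2.e and E3.c say bupivacaine.

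The cost is protocol wording, one form page and the unmasking route, which is the small downside. Whether recording duties must be rearranged cannot be judged, because the recorders are not identified. If the consent form already withholds the drug name, step 1 for patients is only a matter of alignment. Sample size and treatment are unchanged.
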